The proposed sample size (n=80; 40 per arm) will yield more than 80% power to detect effect sizes 0.64 or larger in a two-tailed, two-sample contrast of group-level means, consistent with our primary analysis plan to assess acute treatment effect (4-day) of exogenous ALLO compared to placebo. Furthermore, this approach avoids a priori presumptions to be made on data distribution and impact of potential covariates (i.e., linear vs. non-linear relationship with the outcome). We conservatively based our anticipated estimates on published effect sizes for progesterone-associated or ALLO-induced changes in behavioral, circuit-based, molecular, and physiological measurements of the RDoC Negative Valence System and Arousal and Regulatory System domains, and when none were available, on our own pilot data. While the sample size justification uses a cross-sectional approach as if there is one measurement per participant, the data and analyses will be longitudinal – accounting for repeated measured per participant, which also will increase power and precision. Therefore, we expect that this mixed-model analytic approach will yield even greater statistical power than the conservative estimates from the simpler approach used for sample size determination.

For all primary contrasts, effect sizes estimated from either previous reports or our own preliminary data were large ($d \geq 0.8$). Specifically, for **Aim 1**: the effect of progesterone on rumination assessed using MADRS Item 9 (Pessimistic Thoughts) and the Beck Depression Inventory (BDI) subscore from Items 5 and 8 (Guilt and Self-incrimination, respectively) were large (Cohen's $d > 0.95$), an effect size that is consistent with previously reported⁴⁸, effects of exogenous ALLO on depression symptom ratings using the HDRS-17 being large (Cohen's $d > 1$), as will be investigated in **Aim 3**. Progesterone's effects on attentional bias to negative stimuli as well as functional connectivity are estimated from our preliminary data to be large ($d > 1$). **Aim 2**: Progesterone's effects are estimated from our preliminary data to be large on both BDNF and the inflammation index (derived from CRP, TNF- α , and IL-6 levels) ($d \geq 0.8$). Effects of progesterone on NAA levels in the medial prefrontal cortex, estimated from our preliminary data, and EEG-derived WASO, estimated from a previous report⁴⁹ of exogenous progesterone on sleep parameters in postmenopausal women, are both large ($d > 1$). For Aim 3: Based on prior reports and our preliminary data, our sample size (n=80; 40 per arm) will yield more than 80% power to detect select mediation as identified above.

10. Monitoring and Quality Assurance

This mechanistic intervention study will be conducted as a single-site inpatient randomized placebo-controlled trial using an agent that is FDA approved for women with a hormonally based depression in a new population of women who also have a hormonally based depression. The dose and method of administration—60-hour infusion of brexanolone—will be identical to the marketed agent. Research participants will be closely monitored for adverse events by physicians and nurses in the CCI research unit and by our experienced investigative team, which together participated as a site for the Sage Therapeutics PPD Phase 2 clinical trials using SAGE-547 (now FDA-approved as brexanolone). To minimize risks during the infusion, the FDA-approved Risk Evaluation and Mitigation Strategy (REMS) for brexanolone¹ will be strictly adhered to by our hospital clinical staff on the IPM Unit, consistent with procedures we implemented during the SAGE-547 trial. Safety monitoring will include frequent nursing checks, continuous oxygen saturation by pulse oximetry monitoring, and

administration of the Richmond Agitation Sedation Scale (RASS) for specific attention to sedation and loss of consciousness.

Data and Safety Monitoring Board (DSMB)

The Data and Safety Monitoring Board (DSMB) will have primary safety monitoring oversight for this protocol. As per guidance from the National Institute of Mental Health (NIMH) Human Research Protection Branch (HRPB), this protocol will be monitoring via a formal DSMB. The DSMB is comprised of a group of individuals who are qualified, not directly involved with the design and conduct of the study, and who are objective, without conflict of interest. Their focus is on participant safety, tolerability of study procedures, and adverse events.

To form the DSMB for this trial, our research team will expand upon an established Safety Monitoring Group (SMG) that [name] used for prior studies involving mechanistic intervention and experimental procedures, consistent with these regulatory guidelines. The DSMB will review the proposed project at ongoing regular meetings held at least two times a year, approximately every 6 months. The DSMB will comprise two research physicians and one statistician who are familiar with clinical research, the study medications and their side effects but who are not collaborators or close colleagues of the MPIs or co-Investigators. The two physicians are [REDACTED] a neuro-endocrinologist at Massachusetts General Hospital with expertise in neurosteroids in relation to mood and reproductive transitions and [REDACTED] a psychiatrist at Weill Cornell Medicine with expertise in reproductive psychiatry. Drs. [REDACTED] will review all adverse events and unanticipated problems that arise during the study. A third DSMB member, [REDACTED], will join Drs [REDACTED] to round out the committee to include biostatistical expertise. Dr. [REDACTED] is an Associate Mathematician working in the Brigham and Women's Hospital Division of Sleep and Circadian Disorders.

Blinded outcome and safety data will be reported to the DSMB in open sessions when the study team is present. At the request of the DSMB, closed sessions will be scheduled to review unblinded data, adverse events, and unanticipated problems with only the unblinded statistical expert. The DSMB will also provide direction about early termination of the study should significant safety concerns arise to warrant such consideration. Consistent with local guidelines, all adverse events, including serious adverse events, and unanticipated problems will be managed and reported to our local Institutional Review Board (IRB).

We will adhere to the NIMH Policy on Reportable Events and ensure the timely report of any of the information that falls within this policy (<https://www.nimh.nih.gov/funding/clinical-research/nimh-reportable-events-policy>) to the NIMH Program Officer.

Additional Safety Monitoring and Adverse Event Reporting: While the DSMB has the primary safety monitoring oversight role, this protocol will have additional safety checks that are routinely built into [name] experimental study procedures and those of the IPM Unit. These include routine weekly monitoring of all safety assessments, laboratory studies, and adverse events by designated Study Physicians for this study protocol. In addition, there is a team of physicians who round on all participants during inpatient study procedures in the CCI's IPM. This team coordinates research admissions for [name] studies, including previously for the SAGE-547 (now FDA-approved as brexanolone) PPD trial. The team includes an endocrinologist who will provide additional safety checks as the admitting physician and will be available for questions about safety concerns. During the inpatient admission, nurses will monitor the research participants by following the FDA-approved Risk Evaluation and Mitigation Strategy (REMS) for brexanolone as described above.

Monitoring of Accrual and Retention: Eligible participants will be pre-screened by phone using an IRB-approved questionnaire to inquire about the likelihood of meeting inclusion/exclusion criteria prior to scheduling an in-person screening visit. A tracking sheet with identifying information indicating whether or not they met eligibility will be kept separate from all other study files and saved on a secured server.

Once informed consent is documented, data will be acquired and stored as noted below. We will keep track of all participants who are consented and screened including those who are screen failures. A separate database will house the data from any participant who is eligible to be randomized, as these data will be included in final statistical analyses. Any attrition over the course of the trial will be documented with the reason for discontinuation if known. If not known, these participants will be coded as lost to follow up. These numbers will be reported to the Safety Monitoring Group at each

convened session.

Once randomized, we will be vigilant to minimize loss of data due to the failure of participants to complete all measures. Research staff are trained to check all measures at the time the data are collected to ensure that all items are filled out completely and correctly. For missing data identified at the time data are collected, participants will be asked to promptly provide the necessary missing information unless that indicate their desire not to answer those items.

Data Integrity: All data management activities will be centralized. Standard procedures are used for protocol and form development, data entry, data reconciliation, data editing, database updating, database closure, data retrieval, statistical computing, data security, and confidentiality. An electronic database (REDCap) will serve as the master database for this study. All questionnaire data are collected using standard measures. Those questionnaires completed on paper will be entered by research staff into the REDCap database in a timely manner. Discrepancies will be identified and reconciled. Data that are entered directly into the electronic database either by research staff or by participants via electronic survey mode are validated against appropriate formats and acceptable ranges of responses set for each variable that assure data are accurately entered. Data entry procedures within REDCap will use data checking routines that are executed automatically during the entry process. Finally, summary reports of descriptive statistics will be generated on a regular basis to examine for statistical outliers. All data will be archived and backed-up on a nightly basis on secure servers.

11. Privacy and Confidentiality

- Study procedures will be conducted in a private setting
- Only data and/or specimens necessary for the conduct of the study will be collected
- Data collected (paper and/or electronic) will be maintained in a secure location with appropriate protections such as password protection, encryption, physical security measures (locked files/areas)
- Specimens collected will be maintained in a secure location with appropriate protections (e.g. locked storage spaces, laboratory areas)
- Data and specimens will only be shared with individuals who are members of the IRB-approved research team or approved for sharing as described in this IRB protocol
- Data and/or specimens requiring transportation from one location or electronic space to another will be transported only in a secure manner (e.g. encrypted files, password protection, using chain-of-custody procedures, etc.)
- All electronic communication with participants will comply with Mass General Brigham secure communication policies
- Identifiers will be coded or removed as soon as feasible and access to files linking identifiers with coded data or specimens will be limited to the minimal necessary members of the research team required to conduct the research
- All staff are trained on and will follow the Mass General Brigham policies and procedures for maintaining appropriate confidentiality of research data and specimens
- The PI will ensure that all staff implement and follow any Research Information Service Office (RISO) requirements for this research
- Additional privacy and/or confidentiality protections

Confidentiality Protections

Since information of a personal nature is being collected, there is a risk of loss of confidentiality. All subject data will be entered into Research Electronic Data Capture (REDCap), a HIPAA compliant web-based application hosted by Mass General Brigham, Research Information Science & Computing (RISC). Only research staff listed on the approved IRB protocol with specific permissions will have access to the database. Participants will only be identified with a numerical code in compliance with HIPAA regulations. Moreover, participants will be apprised of their ensured confidentiality and told that clinical data collected from them will be included in an electronic database for research analysis using only a deidentified subject ID.

As with any electronic data storage and transmission, there is a possibility that databases may be hacked. Given that REDCap encrypts all data transmissions and data will be de-identified, these risks are very low.

12. References

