2. SPECIFIC AIMS AND OBJECTIVES

We propose to test the effects of exogenous ALLO in a well-characterized cohort of women with mild to severe depression presenting during early and late perimenopause. This project will use an experimental placebo-controlled, mechanistic trial to determine acute and durable effects of exogenous ALLO on behavioral, cognitive, circuit-level, physiological, and molecular processes centered on the Negative Valence Systems and Arousal and Regulatory Systems Domains of the Research Domain Criteria (RDoC) framework. We expect to uncover neurobiological mechanisms that underlie depression during early and late perimenopause via three aims:

Aim 1: To determine the impact of allopregnanolone on key behavioral and circuit-based processes that underlie depression in perimenopausal women.

Hypotheses: Compared to placebo, exogenous ALLO will improve the following: **1a) behavioral/cognitive** measures of rumination and attentional bias toward negatively valenced external stimuli; and **1b) neurocircuitry**, via resting-state connectivity underlying rumination and negative attentional bias within the default mode network and between the default mode and salience networks.

Aim 2: To determine the impact of allopregnanolone on key molecular and physiological processes that underlie depression by indexing markers of neuroprotection, peripheral inflammation, and sleep physiology in perimenopausal women.

Hypotheses: Compared to placebo, exogenous ALLO will improve the following: **2a) neuroprotection**, via circulating levels of brain-derived neurotrophic factor (BDNF), and levels of N-acetyl-aspartate (NAA) in the medial prefrontal cortex, measured with magnetic resonance spectroscopy; **2b) inflammation**, via circulating levels of pro-inflammatory molecules; and **2c) sleep physiology**, via EEG-derived wakefulness after sleep onset.

[figure not shown]
Exploratory Aim 3: To identify mediators and moderators of the impact of allopregnanolone on clinically-defined global measures of depression severity in perimenopausal women.

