Analysis Plan: Briefly, primary analyses will compare exALLO and placebo subject-level response profiles from baseline to 4-day in each primary outcome to examine acute effects. Secondary analyses will compare exALLO and placebo subject-level response profiles from baseline to 30-day in those same outcomes to examine durability of effects. Analyses of secondary outcomes will be conducted in parallel with those for primary outcomes. Key covariates (e.g., age, race, body mass index, socioeconomic status and stressful events) will be measured and considered a priori as potential predictors in multivariate analyses to reduce unexplained variability. Analytic outcomes can be transformed as needed to satisfy model assumptions such as normally distributed residuals for linear models or, alternatively, non-linear distribution models (e.g., negative binomial, lognormal, or gamma) can be applied in the generalized linear mixed model approach to model the observed distribution of the outcome. Model selection will be based on Akaike information criterion or quasi-likelihood under the independence model criterion values. We will use the False Discovery Rate (FDR) correction⁴⁵, which allows for robust retention of alpha to remain at 5% for each statistical test with the additional constraint of q-threshold also set to 5% (i.e., acceptable FDR of 5%). This analytic approach is advantageous over Bonferroni adjustment and other approaches that adjust the 5% alpha threshold as it will not increase the chance of inflating Type II error given the number of primary outcomes in Aims 1 and 2.

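### The stated power of more than 80% at d = 0.64 is for one unadjusted 5% test at 40 per arm; under the plan's own FDR rule it is about 78% at best, and lower for imaging outcomes if fewer women are scanned

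*Combined protocol and SAP*

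**What the plan says.** The relevant text is in section 9 (Statistical Analysis), with the outcomes in section 2 and the numbers of women in section 4.

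- **Multiplicity.** The FDR correction, cited to Benjamini and Hochberg, "allows for robust retention of alpha to remain at 5% for each statistical test with the additional constraint of q-threshold also set to 5" per cent. The text adds: "This analytic approach is advantageous over Bonferroni adjustment and other approaches that adjust the 5% alpha threshold", on the ground that it does not inflate Type II error "given the number of primary outcomes in Aims 1 and 2". The outcomes in the family are neither listed nor counted.
- **Power.** With 40 women in each arm, the sample is said to be one that "will yield more than 80% power to detect effect sizes 0.64 or larger in a two-tailed, two-sample contrast of group-level means". The plan then ties this figure to the main comparison by calling it "consistent with our primary analysis plan to assess acute treatment effect (4-day) of exogenous ALLO compared to placebo". The basis is disclosed: "While the sample size justification uses a cross-sectional approach as if there is one measurement per participant". The plan expects the longitudinal model to do better than this.
- **Expected effects.** "For all primary contrasts, effect sizes estimated from either previous reports or our own preliminary data were large", meaning d of at least 0.8; for connectivity and NAA the plan gives d above 1.
- **Outcomes.** Section 2 names rumination, attentional bias, connectivity "within the default mode network and between the default mode and salience networks", BDNF, NAA, inflammation and EEG wakefulness after sleep onset.
- **Numbers with data.** Section 4 expects about 40 per arm with usable data for the acute primary outcomes. Sections 4 and 6 make the MRI/MRS visits optional, and section 4 gives MRI its own exclusions. No expected number of scans is stated.

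**The concern.** Two things do not fit together. First, the power statement is presented as matching the primary analysis, but it uses a plain 5% test, whereas each mechanism will be declared positive only if it also passes q of 5%. The sentence on alpha hides the difference by saying that the per-test level is unchanged. Second, the power statement uses 40 per arm for every outcome, although connectivity and NAA depend on scans that a participant may decline or be excluded from.

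At stake is the accuracy of a stated design property. Aims 1 and 2 judge each mechanism separately, so a reader will take 0.64 as the smallest effect the trial can reliably detect on each one. A null connectivity or NAA result would be read against that figure.

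**Working it through.** **Inputs from the documents.** n = 40 per arm, d = 0.64, two-sided, two-sample comparison of means, alpha 5%, q 5%, one measurement per participant (section 9).

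**Assumptions.** The family has m = 7 or 8 outcomes, according to whether connectivity counts once or twice, with inflammation as the single index described in section 9. Outcomes are independent unless stated. Scan numbers below 40 per arm are illustrations.

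**1. Reproduce the plan's figure.** The noncentrality is d × √(n/2) = 0.64 × √20 = 2.862, with 78 degrees of freedom and a critical t of 1.991. Power from the noncentral t distribution is 80.7%. The effect giving exactly 80% is d = 0.634. So the plan's figure is correct for one unadjusted test. At 39 per arm it is 79.7%.

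**2. The working cutoff under Benjamini-Hochberg.** The k-th smallest p-value is compared with (k/m) × 0.05. For m = 7 the cutoffs run from 0.05/7 = 0.71% to 5%; for m = 8, from 0.05/8 = 0.63% to 5%. The 5% cutoff applies only when all m outcomes are rejected. The FDR rejections are therefore always a subset of the unadjusted 5% rejections.

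**3. Power under the stated rule, 40 per arm** (simulation, 200,000 replicates; power averaged over the responding outcomes):

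| Outcomes that respond | d = 0.64, m = 7 | d = 0.64, m = 8 | d = 0.8, m = 7 | d = 0.8, m = 8 |
|---|---|---|---|---|
| All | 78% | 78% | 94% | 94% |
| Four | 70% | 68% | 90% | 89% |
| One | 55% | 53% | 80% | 78% |

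If outcomes correlate at 0.3 and all respond, power at d = 0.64 is 76%. The effect detectable with 80% power, all responding, is 0.656 (m = 7) or 0.655 (m = 8), against 0.634 unadjusted. For comparison, Bonferroni power at d = 0.64 is 54% (m = 7) or 52% (m = 8).

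**4. Does the unlisted family matter to the 78%?** No. With all outcomes responding, power at d = 0.64 is 77.7% to 78.4% for any family size from 3 to 8, which also covers a separate family for each aim.

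**5. Imaging outcomes** (2 of 7 or 3 of 8), all outcomes responding, the others at 40 per arm:

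| Scanned per arm (assumed) | d = 0.64, no FDR | d = 0.64, with FDR | Detectable d at 80%, with FDR | d = 1, with FDR |
|---|---|---|---|---|
| 35 | 75% | 71–72% | 0.70 | 98% |
| 30 | 68% | 64% | 0.75 | 97% |
| 25 | 60% | 55% | 0.82 | 93% |

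Most of this loss comes from fewer scans. At 30 per arm, going from 80.7% to 68% is the scan number; only the further step to 64% is FDR.

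**The case against.** The strongest reply has five parts.

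- **The sentence is true as written.** It describes a two-sample comparison on a declared cross-sectional basis, and that gives 80.7%. This stands, but the same sentence ties the figure to the primary analysis plan, and that plan includes q of 5%.
- **The loss is small and lies where the plan does not expect to be.** It is about 3 points at d = 0.64, and power at d = 0.8 is 94% if all respond. This stands. It limits the seriousness of the point without making the stated floor correct.
- **The mixed model will recover it.** It may. With efficient baseline adjustment, all responding and m = 7, FDR power at d = 0.64 is about 82% if the baseline-to-day-4 correlation is 0.3 and about 90% if it is 0.5. A plain change-score contrast beats the cross-sectional one only above a correlation of 0.5. The plan states no correlation, so the offset cannot be credited as it stands.
- **The alpha sentence can be read as a double rule,** p of at most 5% and q of at most 5%. On that reading the q condition always governs, because a Benjamini-Hochberg adjusted p-value is never below the raw one. So 5% is a ceiling and not the level of each test. The Type II remark is correct as a comparison with Bonferroni, but not against an unadjusted test.
- **The joint family and the scan numbers are inferred.** True. With a separate family for each aim (3 or 4 outcomes), power when only one outcome responds is 63–67%, not 53–55%. The imaging loss arises only if fewer than 40 per arm are scanned, which section 4 does not anticipate. What remains is that optional scans with their own exclusions have not been reconciled with 40 per arm.

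**Conclusion.** The point holds as a should-fix correction to the reported power; it is not a design failure. The figure of more than 80% at d = 0.64 belongs to one unadjusted 5% test. Under the plan's FDR rule, on its own cross-sectional basis, the most favourable case at 40 per arm (independent outcomes, all responding) is about 78%, and the detectable effect is about 0.655. Power is lower if outcomes are correlated or only some respond. The claim that alpha stays at 5% for each test is wrong under Benjamini-Hochberg.

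For connectivity and NAA the figure is lower again if some women are not scanned: about 71–72%, 64% and 55% at an assumed 35, 30 and 25 per arm. At the effects the plan expects, power remains high: 94% at d = 0.8 with 40 per arm and all responding, and 93% or more at d = 1 for imaging outcomes even at 25 per arm. The 78% does not depend on the exact family size; the partial-response figures do.

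**What to change.** 1. List the Aim 1 and 2 primary outcomes that form the FDR family, say whether connectivity counts once or twice, and say whether the two aims are corrected together.
2. Label 0.64 as unadjusted, single-test power at 40 per arm. Add power or detectable effect under Benjamini-Hochberg, leading with the case where all outcomes respond and giving partial response as sensitivity.
3. State how many women per arm are expected to have usable scans, compute the connectivity and NAA figures at that number, and reconcile it with the roughly 40 per arm in section 4. The 25 to 35 per arm used here are illustrations, not values to insert.
4. Delete the claim that alpha stays at 5% for each test. Say instead that Benjamini-Hochberg costs less power than Bonferroni but more than no adjustment.
5. If the mixed-model gain is cited as an offset, state the assumed within-subject correlation and which standard deviation standardises d.

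The cost is one sentence listing the family, two reworded sentences and one line of power figures. The stated detectable effect becomes slightly less favourable (0.634 to about 0.655, and larger for imaging outcomes if fewer women are scanned). No extra participants and no design change are needed.

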- The 60-hour brexanolone vs placebo infusion will begin in the evening of the 2nd inpatient night and end on the last morning immediately preceding post-treatment assessments
- Safety assessments will be conducted daily throughout the infusion and inpatient stay
- 2 electroencephalography (EEG) recordings (one before infusion and one during the final night of the infusion)
- At least once daily assessments of rumination, attentional bias, psychomotor vigilance, mood state (POMS), and depressive symptoms (before and after the infusion)
- Daily blood draws (before and after the infusion). Blood will be collected to run assays, including brain derived neurotrophic factor (BDNF), inflammatory biomarkers, reproductive hormones, serum ALLO levels, and serum for future analyses.
- One urine collection at admission for HCG, one at morning void after first night for melatonin. If there happens to be overnight voiding on first night additional samples will be requested but there is no scheduled collection, it will only be done if the participant is awake to void on their own.

Optional post-admission MRI Visit: resting-state functional MRI (rfMRI) / magnetic resonance spectroscopy (MRS) scans (after the infusion)

Interim Follow-Up and Remote Visit: During the 1-month follow-up period after participants are discharged from the inpatient visit, participants will be asked to complete daily monitoring of their sleep, VMS, and menstrual cycle patterns.

One remote interim visit approximately 2 weeks after the inpatient visit will take place to monitor adverse events, administer the C-SSRS, and assess mood state (POMS) and depressive symptoms.

Follow-Up In-Person Visit: Approximately 30 days after treatment initiation, participants will have a final follow-up in-person visit, during which they will undergo:

- Adverse event and safety monitoring
- Optional rfMRI/MRS scanning procedures
- Behavioral assessments including depressive symptom severity, mood state (POMS), rumination, and attentional bias, psychomotor vigilance; and
- Blood draw for neuroprotective and inflammatory biomarkers, reproductive hormones, ALLO levels, and serum for future analyses.

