The primary analyses to test the hypotheses listed in Aims 1 and 2 will compare allopregnanolone and placebo subject-level response profiles from baseline to 4-day visit for each primary outcome using linear or generalized linear mixed models. Estimation of the fixed effects will allow comparison of means. Fixed effects will include treatment condition and time (baseline, 4-day, 30-day). Subject-level random effects will be modelled by including a random intercept. While linear or generalized linear mixed models provide a robust approach to handling inter-individual variability in response, we will also incorporate additional exploratory analyses to address this concern. To achieve this, we will examine our data using the interclass correlation coefficients (ICC) obtained from the R correlation matrix of the mixed-model regressions. A low ICC value will indicate that intra-individual variability in response is high relative to inter-individual variability, whereas a high ICC value will indicate that there is high inter-individual variation in response relative to intra-individual variability. Additionally, we will estimate subject-specific effects (i.e., slopes in response profiles of each subject from baseline to day 4, estimated by the random effect in the mixed models) and the distribution of subject-specific response magnitude. As exploratory analytic approaches, these subject-specific response magnitudes will be further modelled using baseline participant characteristics (e.g., age, prior history of depression) to elucidate potential physiological and neurophysiological predictors. We expect that these additional exploratory analyses will provide preliminary data on the distribution of participant-specific responses to ALLO, which will inform future studies and analyses. For **Aim 3**, the objective is two-fold: (1) we will assess mediation of improvement in clinically-defined global measures of depression severity by changes in Aim 1 and 2 outcomes, and (2) test effect modification of exogenous ALLO on improvement in clinically-defined global measures of depression severity by (i) the presence/absence of a history of depression recurrence, and separately, ii) perimenopausal factors (early vs. late perimenopause). In addition to the mediation pathways described above, we recognize that the possible pathways linking ALLO to depression are likely more numerous than these predefined mediation pathways. Therefore, we plan to further explore other putative pathways using partial least squares structural equation modeling. We will identify combinations of variables (features) that cluster together (factors) as latent variables, and then quantify the strength of their relationships based on factor loading (correlation between each feature and each factor). We will develop primary mediation models for 4-day effects and then 30-day secondary effects in

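### The primary arm comparison is baseline to day 4, but the listed mixed model names no treatment-by-time term or day-4 contrast and does not say how baseline is handled

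*Combined protocol and SAP*

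**What the plan says.** All references are to section 9 (Statistical Analysis) of the combined protocol and SAP unless stated.

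- Primary comparison: "primary analyses will compare exALLO and placebo subject-level response profiles from baseline to 4-day in each primary outcome to examine acute effects".
- Secondary comparison, kept separate: "Secondary analyses will compare exALLO and placebo subject-level response profiles from baseline to 30-day in those same outcomes to examine durability of effects".
- Model for Aims 1 and 2: "Fixed effects will include treatment condition and time (baseline, 4-day, 30-day). Subject-level random effects will be modelled by including a random intercept". Baseline is a level of time, so it enters as a repeated response. The next step is described only as a comparison of means from the fixed effects.
- Covariates: the examples given do not include the baseline value of the outcome.
- Interactions: the only ones written are modifier by treatment, for Aim 3.
- Sample size: 40 per arm gives more than 80% power at an effect size of 0.64, treating the data as one measurement per participant, "consistent with our primary analysis plan to assess acute treatment effect (4-day) of exogenous ALLO compared to placebo". It adds that "we expect that this mixed-model analytic approach will yield even greater statistical power than the conservative estimates from the simpler approach".
- Anticipated effects: "For all primary contrasts, effect sizes estimated from either previous reports or our own preliminary data were large" (d of 0.8 or more; above 1 for WASO).
- Exploratory subject-specific effects: "slopes in response profiles of each subject from baseline to day 4, estimated by the random effect in the mixed models".
- Section 6, four-night inpatient visit: "2 electroencephalography (EEG) recordings (one before infusion and one during the final night of the infusion". WASO therefore has two measurements, not three.

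**The concern.** A model with treatment, time and a random intercept has a single treatment coefficient, common to all visits. It cannot express a difference between arms that is absent before the infusion and present at day 4, and it merges the acute and durable effects that the plan separates.

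If a treatment-by-time term is assumed, a second choice stays open: baseline means may be free in each arm, constrained equal, or replaced by adjustment for the baseline value. These target the same day-4 effect but differ in power, and the plan's expectation that the mixed model improves on the cross-sectional calculation depends on which is used. The choice affects the primary test of every Aim 1 and 2 outcome and is left to the analyst.

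A smaller point concerns the exploratory analyses only. A random intercept shifts a subject's whole profile up or down; it does not give subject-specific slopes from baseline to day 4.

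**Working it through.** **Inputs from the documents.** 40 per arm, 1:1, two-sided 0.05, d = 0.64 (section 9, sample size); anticipated d of 0.8 or more; 72 of 80 women at day 30 (section 4).

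**Assumptions not in the documents.** Within-subject correlation ρ of 0.3 to 0.7; day-30 effect from 0 to 100% of the day-4 effect; d in units of the single-visit SD; equal variances and a linear scale. Equal correlation between visits follows from the listed random intercept. Power is before the FDR correction.

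**Method.** Noncentral t with noncentrality δ / √(V × 2/40), where δ is what the contrast estimates and V its variance factor.

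**1. The plan's own figure.** δ = 0.64, V = 1: noncentrality 0.64 × √20 = 2.86, 78 df, power 80.7%. This reproduces the stated figure. At d = 0.8 power is 94.2%. The smallest d detectable with 80% power is 0.63.

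**2. Treatment-by-time, free baseline means.** The day-4 interaction equals the difference in unadjusted change, with V = 1 + 1 − 2ρ = 2(1 − ρ). This exceeds 1, and so does worse than the cross-sectional test, whenever ρ < 0.5.

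**3. Treatment-by-time, baseline constrained equal or adjusted for.** V = 1 − ρ², with 77 df. This is below 1 at any nonzero ρ. It is also below 2(1 − ρ) at any ρ < 1, because 1 − ρ² = (1 − ρ)(1 + ρ).

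| Day-4 contrast | ρ = 0.3 | ρ = 0.5 | ρ = 0.7 |
|---|---|---|---|
| Free baseline, d = 0.64 | 66.6% | 80.7% | 95.4% |
| Constrained or adjusted, d = 0.64 | 84.2% | 90.4% | 97.7% |
| Free baseline, d = 0.8 | 84.8% | 94.2% | 99.5% |
| Constrained or adjusted, d = 0.8 | 95.9% | 98.3% | 99.9% |
| Detectable d at 80%, free | 0.75 | 0.63 | 0.49 |
| Detectable d at 80%, constrained or adjusted | 0.61 | 0.55 | 0.45 |

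Generalized least squares with 36 per arm at day 30 gives the same variances for the day-4 contrast.

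**4. The listed terms alone (the plan does not say this will be fitted).** With three complete visits, the coefficient estimates (0 + d4 + d30)/3 with V = (1 + 2ρ)/3. For d4 = 0.64 it targets 0.64/3 = 0.213 if the effect is gone by day 30, and 1.28/3 = 0.427 if it persists fully. Power runs from 18% (ρ = 0.7, no persistence) to 73% (ρ = 0.3, full persistence). At d4 = 0.8 the range is 26% to 90%. With 36 per arm at day 30 the ranges are 20% to 71% and 28% to 88%.

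For WASO, with two recordings, the coefficient is d4/2 and V = (1 + ρ)/2. At d = 1.0 power is 78%, 72% and 67% for ρ = 0.3, 0.5 and 0.7, against 99% for the day-4 contrast.

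**5. Subject-specific slopes.** A random-slope model has four variance parameters: intercept, slope, their covariance and residual. Two WASO recordings supply three moments (two variances and one covariance), so the model is not identified for that outcome.

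**The case against.** The strongest reply is that comparing response profiles between arms over time already is a treatment-by-time comparison. The plan separates day 4 from day 30 throughout, and its list of fixed effects need not be exhaustive. That is fair. The text does not prove that an additive model will be run, and the figures in step 4 are only conditional. But the reply does not settle baseline handling, which has to be decided because baseline is a level of time.

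Three further objections limit the numbers:

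- The one-third weighting needs complete data, a linear scale and equal correlation between visits. The last follows from the listed random intercept, but the plan also mentions a residual correlation matrix and allows non-normal models. Another structure would change the weights; AR(1) with ρ = 0.5 gives 0.4, 0.2 and 0.4.
- The loss with free baseline means assumes d is scaled to the single-visit SD. The plan's cross-sectional framing supports that, but it does not name the standardiser. If d were scaled to the SD of change, the change contrast would keep 81% at d = 0.64 whatever ρ is.
- Free baseline means are valid under randomization, and the open covariate list does not exclude baseline adjustment. The case for constraint or adjustment is efficiency, not bias.

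These limit the size of the consequence. The omission stands.

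**Conclusion.** The concern holds and should be fixed. The plan states its primary comparison but names no model term or contrast that delivers it, and it does not say how baseline means are treated. Confidence in the textual gap is high; the size of its effect depends on the assumptions above.

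At d = 0.64 and ρ = 0.3, the choice between free and constrained or adjusted baseline means moves power from 67% to 84%. The expectation of more power than the cross-sectional calculation fails with free baseline means when ρ is below 0.5, and holds with constraint or adjustment at any nonzero ρ. At d = 0.8 the lowest baseline-to-day-4 option has 85% before FDR, so the trial is not shown to be underpowered. The slope statement does not match the listed random intercept, but it affects no primary test.

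**What to change.** In section 9, specify for Aims 1 and 2:

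- Categorical time with a treatment-by-time term, and either baseline means constrained equal across arms or baseline as a covariate with only post-infusion visits as outcomes. Either is acceptable.
- The day-4 treatment contrast as primary and the day-30 contrast as secondary.
- For WASO, the final-night recording adjusted for the pre-infusion recording.
- For the exploratory subject-specific responses, observed baseline-adjusted change in place of random-effect slopes, or random slopes only where the data support them, which excludes WASO.

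The power statement should then name the baseline handling it relies on. The cost is SAP wording only: no new data, visits or participants.
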